In-depth qualitative interviews with stimulant-using MSM. In-depth interviews with stimulant-using MSM will be approximately one hour and cover topics such as history of stimulant use, attitudes and beliefs about PrEP. Those who are not on PrEP will be asked to describe on barriers and facilitators to accessing PrEP. Those who are currently taking PrEP will be asked to describe how they successfully

IRB Study Number: 20180823

Version #10.1; April 2023

navigated the process of initiation and strategies they are implementing to achieve prevention effective PrEP adherence. After completing the interview, participants will complete a brief survey to assess demographic information and efforts to navigate the PrEP healthcare continuum (see attached). Stimulant-using MSM will receive \$40 for completing this one time study visit.

[figure not shown]
Phase II – We will conduct a pilot SMART with 70 HIV-negative, stimulant-using MSM who meet CDC criteria for PrEP eligibility.

First Stage Intervention. After completing a baseline assessment and a brief run-in period, participants will be randomized to complete a 3-month CM intervention or a two-session MI intervention that were developed as part of our Phase I activities.

Second Stage Intervention. Three months after this first-stage randomization, participants will complete a second informed consent prior to a 3-month follow-up assessment to determine whether they are responders.

[figure not shown]
Experimental Conditions. Responders will be classified as those who have started PrEP, the primary outcome. Responders will continue with assessments only.

Participants who have not responded to the initial intervention will be randomized again to either: 1) continue with assessments only; or 2) switch to the other intervention (i.e., CM+MI versus MI+CM). An overview of the pilot SMART procedures is provided in the figure below. Below we describe each of the procedures relevant to executing this pilot SMART.

Telephone screen. Stimulant-using MSM will complete a brief telephone screen to determine eligibility for enrolling in the pilot SMART based on inclusion criteria above for Phase II (see attached). This telephone screen has been modified to include items relevant to the novel coronavirus (COVID-19), which are also attached. The figure below describes the participant flow for the pilot SMART.

PRISM 2.0 Study Flow Diagram

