Stage 2 informed consent. Prior to completing the 3-month follow-up assessment, participants will provide informed consent for the Stage 2 of the pilot SMART. This consent will clarify that participants may be invited to participate in a CM or MI intervention based on the responses to the survey questions and prior intervention assignment. Due to the challenges presented by COVID-19, we are requesting a waiver of written consent to review the consent with participants over zoom.

3-month follow-up assessment with second-stage randomization. After completing the informed consent process, we will re-administer quantitative measures from the baseline assessment via Zoom, and those who have not started PrEP will be classified as non-responders. All non-responders will complete the second-stage randomization to either: 1) continue with assessments only; or 2) switch to the other intervention (CM+MI versus MI+CM). Those randomized to receive CM or MI will receive these intervention consistent with the protocols described above. Responders will continue with assessments only. Participants will receive a \$50 Amazon gift card or secure cash application payment for completing this assessment. Participants will have a 30-day window (+1 month) to complete their follow-up assessments.

6-month follow-up assessment. We will re-administer the quantitative measures from the baseline assessment and a qualitative exit interview (see attached) via zoom. Participants will receive a \$50 Amazon gift card or secure cash application payment for completing this assessment. Participants will have a 30-day window (+1 month) to complete their follow-up assessments.

6) Risks

These study procedures meet the criteria for minimal risk research activities. However, possible risks include: 1) a breach of confidentiality; and 2) negative psychological reactions to study procedures.

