Because this is a pilot study, we have not conducted a formal power analysis. In fact, there is increasing recognition in clinical research methods that pilots should focus primarily upon issues relevant to feasibility and acceptability of a more definitive study, not effect size estimation.

Feasibility. To evaluate feasibility of a more definitive trial, we will monitor rates of recruitment and effort required (e.g. number of staff hours) as well as the number of screenings conducted, proportion eligible, and proportion who agree to enroll. *Feasibility of recruitment* will be operationalized as an enrollment rate of 70% or higher, an established standard in the literature. We will also record number of rescheduled and missed assessment visits, CM visits, and MI sessions to estimate staffing needs and retention protocols for a planned R01. *Feasibility of intervention delivery* will be operationalized as attending three-fourths of scheduled MI sessions (3 of 4 sessions completed on average). Although power will be limited, we will conduct independent samples t-tests to describe the average number of MI sessions attended among non-responders randomized to switch (i.e., CM+MI vs. MI+CM).

Acceptability. To measure *acceptability*, we will modify previous intervention satisfaction evaluation surveys that have been administered to methamphetamine users in [name] clinical research. Measures include items such as, "How satisfied were you with the program in general?" and "How likely are you to recommend this intervention to a friend who uses stimulants?" Independent samples t-tests will describe mean acceptability ratings of CM and MI among non-responders who are randomized to switch (i.e., CM+MI vs. MI+CM).

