PrEP Readiness Interventions for Supporting Motivation

[name], ABAP (Contact MPI) & [name], MPH (MPI)

NCT04205487

August 7, 2024

Feasibility. In this pilot SMART, we examined several indices of feasibility. We report randomization rates, completion of MI and CM sessions, fidelity ratings of MI sessions, and follow-up rates over six months.

Acceptability. After the 6-month assessment, participants were given the opportunity to sit for a one-on-one, semi-structured qualitative exit interview via Zoom. The staff member conducting exit interviews was not involved in the primary study procedures to avoid bias. Participants were given an overview of the activities they completed during PRISM (e.g., two MI sessions, CM incentives, and three surveys) and asked about their experiences. Interview guides were tailored to each participant's study arm (MI, CM, or MI+CM) and whether they had filled a PrEP prescription during the intervention (i.e., responders versus non-responders). Exit interviews were approximately 30 minutes and participants received a \$50 incentive.

Qualitative interviews were analyzed using a rapid qualitative analytic approach as a guide (Hamilton, 2020; Harkness et al., 2022). Interviews were first transcribed verbatim and reviewed for quality assurance. Transcriptions were then used to develop a matrix summary of participant responses, including participant number, intervention arm, PrEP status, and responses to each domain of interest. The research team, consisting of a graduate student research assistant, a doctoral level interviewer and a doctoral level project manager, reviewed and discussed the matrix to identify emerging themes, data consistency and matrix accuracy. Illustrative quotes were then extracted to highlight relevant themes. Finally, the manuscript authors reviewed the matrix, themes, and illustrative quotes as well as agreed upon the accuracy of the findings.

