PRISM primary and secondary outcomes. Adaptive interventions that are embedded in a SMART can be compared via the Weighted and Replicated (W&R) method (Nahum-Shani et al., 2012). However, given the feasibility and acceptability nature of this study we instead descriptively compared three groups by aggregating across the first-stage and second-stage randomizations (see Figure 1): MI-only (arms D and E), CM-only (arms A and B), and MI+CM (arms C and F). Specifically, our efforts to examine the primary and secondary outcomes proceeded in four steps. First, demographic characteristics and meth use severity were stratified by first-stage randomization status (i.e., MI versus CM) to ensure randomization was successful (see Table 1). Second, intervention assignment was collapsed into the three groups described above. Third, because pilot trials do not provide reliable effect size estimates (Kraemer & Kupfer, 2006), we did not conduct statistical tests or comment on the magnitude of CM, MI, or MI+CM effects. Instead, we provide descriptive statistics for primary and secondary outcomes at six months stratified by intervention assignment. Fourth, we examined correlates of verified PrEP use (versus no PrEP use) over the 6-month follow-up, irrespective of first- or second-stage randomization status.

Figure 1. Pilot SMART procedures

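### The SAP's MI+CM group can contain only participants who had not started PrEP at 3 months, so it is not comparable with MI-only or CM-only

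*SAP*

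**What the plan says.** The protocol (section 5, Experimental Conditions) treats participants who have started PrEP as responders, who go on with assessments only. For the rest, the rule reads: "Participants who have not responded to the initial intervention will be randomized again to either: 1) continue with assessments only; or 2) switch". Switching here means receiving whichever of CM and MI was not given first. The paragraph on the 3-month follow-up assessment fixes the timing: at that visit, "those who have not started PrEP will be classified as non-responders". Section 8 (Feasibility) describes the two switch sequences in the same way, referring to MI sessions attended "among non-responders randomized to switch (i.e., CM+MI vs. MI+CM").

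The SAP (PRISM primary and secondary outcomes) names the weighted-and-replicated (W&R) method for comparing embedded adaptive interventions and sets it aside because this is a feasibility and acceptability study. Instead the authors "descriptively compared three groups by aggregating across the first-stage and second-stage randomizations", namely "MI-only (arms D and E), CM-only (arms A and B), and MI+CM (arms C and F"). No statistical tests are run and effect magnitude is not discussed, but "we provide descriptive statistics for primary and secondary outcomes at six months stratified by intervention assignment". The text does not mention that the groups differ in responder status.

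**The concern.** The only route to both interventions is to have not started PrEP at 3 months. A group defined by having received both is therefore selected on an early value of an outcome in the table. The single-intervention groups are selected the other way: they keep every responder and lose the non-responders who switched.

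This is a difference in composition, not imprecision, and a larger sample would not remove it. The affected comparison is MI+CM against either single group. With no intervention difference, MI-only and CM-only have equal expected rates, although each overstates uptake for the first-stage arm it came from.

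Aim 2 (protocol section 2) concerns adaptive strategies that combine CM with MI. Any such strategy includes its first-stage responders, so the MI+CM column represents none of them. The SAP draws no efficacy conclusion, so what is at stake is how a reader, including whoever plans the full-scale SMART, takes the percentages.

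**Working it through.** **Composition.** There are two first-stage arms, each ending in three cells: responder; non-responder with assessments only; non-responder switched. Of these six cells only the two switch cells receive both interventions. Figure 1 is not available in the text, but C and F must be those two cells.

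**Inputs.** N = 70 (protocol section 5). The documents give no uptake rate, allocation ratio or loss rate, so there is no plan figure to reproduce and every rate below is an assumption:
- r = probability of starting PrEP by month 3, the same in both arms
- q = probability of a later start among non-responders, the same whether switched or not (no intervention difference)
- p = probability that a non-responder is switched, 1/2 unless stated
- loss unrelated to response, and none after month 3

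**Cumulative uptake, known 3-month status.**
- Single group: [r + (1−r)(1−p)q] / [r + (1−r)(1−p)]
- MI+CM: q
- Gap: r(1−q) / [r + (1−r)(1−p)], which is 2r(1−q)/(1+r) at p = 1/2

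The gap is positive whenever r > 0 and q < 1, for any p below 1. For r = 15%, q = 30%: 2 × 0.15 × 0.70 / 1.15 = 0.183.

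The first-stage arm's own expected rate is r + (1−r)q. The single group exceeds it by r(1−q)(1−r)/(1+r).

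| r | q | Single group | MI+CM | Gap (points) | Excess over first-stage arm (points) |
|---|---|---|---|---|---|
| 5% | 10% | 18.6% | 10% | 8.6 | 4.1 |
| 5% | 30% | 36.7% | 30% | 6.7 | 3.2 |
| 15% | 10% | 33.5% | 10% | 23.5 | 10.0 |
| 15% | 30% | 48.3% | 30% | 18.3 | 7.8 |
| 30% | 20% | 56.9% | 20% | 36.9 | 12.9 |

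With p = 1/3 or 2/3, the 18.3 becomes 14.7 or 24.2, and the 36.9 becomes 31.3 or 45.0.

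**Participants without 3-month status.** The SAP does not say where participants with no 3-month visit or no Stage 2 consent are placed. Suppose a share L is lost before month 3 and counted as non-starters in the single groups. The gap becomes (1−L)[r + (1−r)q/2] / [L + (1−L)(1+r)/2] − q, and it is zero at L = r(1−q)/[q + r(1−q)].

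| r, q | Gap, L = 15% | Gap, L = 30% | Break-even L |
|---|---|---|---|
| 5%, 30% | −2.6 | −9.8 | 10% |
| 15%, 30% | 6.9 | −2.3 | 26% |
| 30%, 20% | 24.8 | 14.3 | 55% |

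**Current use instead of ever started.** If a share d of responders has stopped by month 6, r in the numerator becomes (1−d)r. At r = 15%, q = 30%, d = 30% the gap is 10.4 points, or 0.9 with L = 15% as well. Without loss it is zero at d = 1−q.

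**PrEP medical evaluation.** If every starter has been evaluated and q now means evaluation among non-responders, the same formula gives 3.8 points (r = 5%, q = 60%), 10.4 (15%, 60%) and 23.1 (30%, 50%). Early retention is plausibly affected too. For condomless anal sex, stimulant use and motivation the direction is undetermined.

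**How often it would show at N = 70.** In simulation with 35 per first-stage arm and no loss, MI+CM is strictly the lowest of the three groups in 0.51 to 0.63 of runs at r = 5% (q = 30% to 10%), 0.83 at (15%, 30%) and 0.99 at (30%, 20%). The benchmark is about 0.3 when all three groups share one rate. With 15% loss counted in the single groups, the figures at (5%, 30%), (15%, 30%) and (30%, 20%) fall to about 0.24, 0.53 and 0.93.

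**Illustration when switching helps.** Take later start as 40% if switched and 30% if not.
- r = 15%: the table is expected to show (0.15 + 0.425 × 0.30)/0.575 = 48.3% against 40.0% for MI+CM. The strategy with the switch is in fact better: 0.15 + 0.85 × 0.40 = 49.0% against 0.15 + 0.85 × 0.30 = 40.5%.
- r = 5%: the table shows 36.7% against 40.0%, which is the correct order.

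**The case against.** The SAP is openly descriptive. It runs no tests, does not discuss effect magnitude, and says W&R was not used. The protocol (section 8) likewise holds that "pilots should focus primarily upon issues relevant to feasibility and acceptability of a more definitive study, not effect size estimation". The groups match the interventions received, which is how the exit interviews use them, and nothing says they estimate a first-stage arm or an embedded strategy. All sizes above are assumed. The direction is shown only for participants with known 3-month status and can reverse with modest loss when early starts are rare. The outcome table itself is not in the documents, and Figure 1 may show which arms are responders. Finer tables would have very small cells and might invite the comparisons the authors disclaim.

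Much of this stands as a limit. The size is unknown, the direction for the table as published depends on where participants with missing status are placed, and no efficacy claim is made. It does not remove the defect. The reasons given for not testing concern imprecision, whereas this is a difference in who can be in each column. The SAP text still describes a comparison of three groups and gives no caveat on composition. That the direction can turn on an unstated placement rule is itself a reason to state the rule.

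**Conclusion.** The concern holds. That MI+CM excludes every 3-month responder follows from the protocol's re-randomization rule and needs no assumption about rates. With known 3-month status and no intervention difference, expected cumulative uptake is lower in MI+CM for any r above 0 and q below 1. Under 1:1 allocation the gap runs from about 7 points (r = 5%, q = 30%) to 37 points (r = 30%, q = 20%) across the assumed rates. For all randomized participants it may be smaller, absent or reversed, depending on early loss, discontinuation and where participants with unknown status are counted. The consequence is a risk of misreading a descriptive table, not a false test result. It should be fixed.

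**What to change.** At minimum:

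1. Split each column of the three-group table into 3-month responders and non-responders, using the protocol's 3-month definition. The SAP's Acceptability section uses a different one, "whether they had filled a PrEP prescription during the intervention (i.e., responders versus non-responders"), with no 3-month limit stated.
2. State under the table that MI+CM contains only 3-month non-responders.
3. Show participants with no 3-month status or no Stage 2 consent separately.

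Also tabulate six-month outcomes (a) by first-stage arm as randomized, with all randomized participants in the denominator, and (b) as switch against assessments only among re-randomized non-responders within each first-stage arm. Both respect the randomization and can stay descriptive. Optionally, give W&R-weighted percentages for the four embedded strategies, with weights from the actual allocation probabilities (2 and 4 if both stages were 1:1). In simulation under no difference, these weights removed the gap.

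When revising, reconcile the primary outcome: protocol section 5 names PrEP start, while section 8 (Quantitative Analyses) names PrEP medical evaluation.

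The cost is a note and a re-tabulation of existing data. The drawback is small cells. With 35 per first-stage arm, expect about 17, 15 or 12 per switch cell and about 2, 5 or 10 responders per arm at r = 5%, 15% or 30%. Approximate 95% intervals for a difference are ±33 points for 15 v 15 at 30%, ±32 for 12 v 12 at 20%, and ±23 for 35 v 35 at 44%. Counts should therefore accompany every percentage.

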MSM who use stimulants have been consistently shown to be at a 3-6 fold greater risk of HIV seroconversion. Despite successful deployment of public health interventions, recent methamphetamine use doubled from 2011-2014 (from 4% to 9%) among MSM in New York City (NYC). This trend is corroborated by comparable increases in methamphetamine use in South Florida and other urban areas such that national rates are meeting or exceeding 2005 peaks. In South

IRB Study Number: 20180823

Version #10.1; April 2023

Florida, the 12-month prevalence of stimulant use is among the highest nationally for MSM: 25% cocaine, 9% ecstasy, 6% crack-cocaine, and 6% methamphetamine. Stimulant use is also prevalent in ethnic minority MSM where HIV incidence is the highest. For example, we recently observed that one-in-five young black MSM in Texas reported stimulant use in the past two months.

Combining CM and MI could optimize HIV prevention in stimulant-using MSM. CM is an evidence-based substance use intervention where individuals receive tangible rewards as positive reinforcement for stimulant abstinence, which targets extrinsic motivation. One enduring concern with CM is the risk for relapse after the incentives are discontinued. Because MI explicitly targets intrinsic motivation, it could have synergistic, beneficial effects on long-term abstinence if delivered with CM. At the same time, MI alone may not adequately address structural factors (e.g., transportation) that are key obstacles to HIV prevention with stimulant-using MSM. CM incentives could amplify the benefits of MI by assisting with navigation of these structural barriers while providing positive reinforcement for behavior change.

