This pilot SMART will focus on testing different schedules for the sequential delivery of these scalable motivational enhancement interventions to target sequentially linked behaviors (i.e., PrEP medical evaluation, PrEP uptake, and early PrEP care retention) to facilitate entry into the PrEP care continuum. In Phase I, we will implement formative qualitative research by conducting key informant interviews with PrEP healthcare team members and in-depth qualitative interviews with stimulant-using MSM. These data will inform our efforts to tailor the CM and MI interventions to simultaneously reduce substance use while optimizing engagement along the PrEP care continuum. In Phase II, we will conduct a pilot SMART of the sequentially delivered CM and MI interventions to examine the feasibility, acceptability, and potential scalability of these motivational enhancement approaches.

4) Inclusion and Exclusion Criteria*

Recruitment: PrEP healthcare team members will be recruited via professional networks of the study investigators to complete key informant interviews regarding barriers and facilitators to delivering PrEP to stimulant-using MSM. We will recruit stimulant-using MSM for in-depth qualitative interviews in Phase I as well as the pilot SMART of the sequentially delivered CM and MI interventions in Phase II. Participants will be recruited from a national sampling frame using social networking applications where men meet romantic and sexual partners (e.g., Scruff, Grindr). We will also recruit participants in South Florida from the community as well as through extant registries of HIV- MSM that are managed by Drs. [name] and [name] at the University of Miami as well as [name] at the City University of New York. More detailed information regarding our recruitment plan is provided below.

IRB Study Number: 20180823
Version #10.1; April 2023

Inclusion Criteria for Phase I: Participants will be included in this project based on:

- 18 years of age or older
- Sexually active MSM
- Reports using methamphetamine, powder cocaine, or crack-cocaine at least one day in the past month
- HIV-negative (self-report)
- Meets CDC criteria for PrEP eligibility

Exclusion Criteria for Phase I: Participants will be excluded if they: a) are under 18 years of age; b) are not a man who has sex with men; and c) are unable to provide informed consent at the assessment visit in English.

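### The SAP's six-month outcome summaries pool the two switch sequences, CM then MI and MI then CM, into one MI+CM group, so neither sequence is described on its own

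*SAP*

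**What the plan says.** **SAP, PRISM primary and secondary outcomes.** The analysis has four steps. Step two collapses assignment into three groups: "MI-only (arms D and E), CM-only (arms A and B), and MI+CM (arms C and F". Step three gives descriptive statistics for the six-month primary and secondary outcomes by assignment, without tests. The reasons given are that this is a feasibility and acceptability study and that effect sizes from pilots are unreliable. On those grounds the SAP also sets aside the Weighted and Replicated method for comparing embedded strategies.

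**Protocol, section 3 (Background).** The focus of the pilot SMART is described as "testing different schedules for the sequential delivery of these scalable motivational enhancement interventions". The same section closes by naming feasibility, acceptability and potential scalability as what the pilot examines.

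**Protocol, section 5 (Procedures Involved).** At the first stage, "participants will be randomized to complete a 3-month CM intervention or a two-session MI intervention". At three months, those who have not started PrEP are randomized either to assessment alone or to "switch to the other intervention (CM+MI versus MI+CM". Responders receive assessments only.

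**Protocol, section 8 (Data Management; Feasibility and Acceptability).** MI sessions attended and acceptability ratings are to be described by sequence, among "non-responders randomized to switch (i.e., CM+MI vs. MI+CM".

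**The concern.** The protocol treats the order of the two interventions as something the pilot should inform, and it names the two switch sequences separately wherever it describes second-stage assignment. The SAP's outcome summaries put them in one group. Its reasons support leaving out tests and the Weighted and Replicated method. They do not explain why two opposite sequences should share a column, because showing them apart involves no test and no claim about effect size.

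Two things are lost. First, a pooled proportion cannot show whether the two sequences had similar or opposite results. Second, the pooled group combines men who did not start PrEP on CM with men who did not start PrEP on MI, in proportions that depend on the two first-stage response rates. The pilot is meant to inform a full-scale SMART (Protocol section 2, Aim 3), whose designers would want the results of each sequence, however imprecise.

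**Working it through.** **Which arms are pooled.** Figure 1 is not shown, so the labels are inferred. Each first-stage intervention leads to three cells: responders, non-responders on assessment alone, and non-responders who switch. That makes six arms, A to F. Only the two switch cells receive both interventions, so the MI+CM group, C and F, must be those two. By the SAP's grouping, C sits with the CM arms (CM then MI) and F with the MI arms (MI then CM).

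**Plan's own figure.** The total comes from Protocol section 5: "We will conduct a pilot SMART with 70 HIV-negative, stimulant-using MSM who meet CDC criteria for PrEP eligibility". Section 8 states: "Because this is a pilot study, we have not conducted a formal power analysis". There is therefore no sample-size calculation to reproduce. The documents give neither allocation ratios nor an expected response rate.

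**Expected arm sizes.** Assume 1:1 allocation at both stages, no loss by month 3, and the same response rate r in both first-stage arms. Each first-stage arm has 70/2 = 35 men, so each of C and F has 35(1 − r)/2 = n and the pooled group has 2n. For scale, the 95% Wald half-width for C minus F, with a true proportion of 30% in both, is 1.96 × √(2 × 0.3 × 0.7 / n).

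| r | n in each of C and F | Pooled MI+CM | Half-width, C minus F (points) |
|---|---|---|---|
| 10% | 15.75 | 31.5 | ±32 |
| 20% | 14 | 28 | ±34 |
| 30% | 12.25 | 24.5 | ±36 |
| 40% | 10.5 | 21 | ±39 |
| 50% | 8.75 | 17.5 | ±43 |
| 60% | 7 | 14 | ±48 |

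With 70-80% non-response, each switch arm has 12.25 to 14 men. Across the whole range it has about 7 to 16.

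**What pooling hides.** With equal cells, C = 20% and F = 60% give (20 + 60)/2 = 40%, the same as C = F = 40% or C = 60% and F = 20%.

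**How the mix can move the figure.** Suppose instead that 40% respond to CM and 20% to MI. Then C has 35 × 0.6/2 = 10.5 men and F has 35 × 0.8/2 = 14. With outcomes of 20% in C and 60% in F, the pooled figure is (10.5 × 0.20 + 14 × 0.60)/24.5 = 10.5/24.5 = 43%, not 40%. Neither sequence has changed; only the first-stage response rates have.

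**The case against.** The strongest objection is that C against F is not a clean comparison of schedules. C holds only men who did not start PrEP on CM, and F only men who did not start it on MI. Conditioning on non-response to different interventions breaks the randomized comparison. Moreover, a full schedule such as starting with CM and adding MI for non-responders also includes its responders. This stands. It limits what separate columns can show and calls for a caution beside them. It does not favor pooling, which combines the same two selected groups without showing either.

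Second, the formal aims are feasibility, acceptability and scalability, and no power analysis was done. The protocol's comparisons by sequence cover only MI sessions attended and acceptability, while its Quantitative Analyses paragraph refers to differences by arm and promises no order contrast. All of this stands. With half-widths of about ±32 to ±48 points, the columns can be described but not usefully tested.

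Third, a reader might argue that the six-month snapshot catches the sequences at different distances from the end of incentives, citing the Background: "One enduring concern with CM is the risk for relapse after the incentives are discontinued". The documents do not support using this as a general argument. That sentence concerns rewards for stimulant abstinence and calls relapse one concern among possible others. CM in this trial pays $50 for a PrEP evaluation and $50 for a filled prescription (section 5). The primary outcome in the Quantitative Analyses paragraph is evaluation at any time in six months, so a man evaluated in month 2 still counts after incentives end. The point here does not rely on it.

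**Conclusion.** The concern holds as a gap in reporting. The SAP's planned six-month summaries of primary and secondary outcomes do not describe CM then MI and MI then CM separately, although the protocol gives delivery schedules as a focus and keeps the sequences apart in sections 5 and 8. The SAP's stated reasons do not cover the merge.

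Two stronger readings should be resisted. A reader might infer that the trial is unable to describe the sequences at all. The documents do not show that: arms C and F remain labelled, the collapse is stated only for primary and secondary outcomes, the SAP does not say that session completion is pooled, and no outcome table is available to inspect. A reader might also infer that splitting C and F would yield a randomized test of order. It would not, because of the selection on non-response.

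The conclusion rests on the inference about arm labels, which the design makes safe for the pair. The cell sizes depend on the assumed allocation, response rates and absence of loss. The percentages used to illustrate masking are hypothetical.

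**What to change.** In steps two and three, report arms C and F as separate columns, with n and counts, for every primary and secondary outcome at six months. Showing all six arms is preferable: a reader can then see each responder arm beside the switch arm that belongs to the same schedule, which C and F alone do not allow. Keep any pooled MI+CM column only as an addition.

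Add a sentence stating that C and F contain only first-stage non-responders, to CM and to MI respectively, so a difference between them is descriptive and cannot be credited to order alone. No test is needed, and the SAP's decision not to test or comment on effect size can stay.

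The cost is two columns in place of one, or six in place of three, from data already held by arm. The downside is small cells, which is why counts should accompany any percentage.

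### Randomized men without a month-3 classification have no stated place in the SAP's three six-month outcome groups

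*SAP*

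**What the plan says.** Protocol section 5 (First Stage Intervention) gives the first randomization: "participants will be randomized to complete a 3-month CM intervention or a two-session MI intervention". Under Second Stage Intervention, three months later, "participants will complete a second informed consent prior to a 3-month follow-up assessment to determine whether they are responders". The paragraph on the 3-month assessment adds that "those who have not started PrEP will be classified as non-responders", and that "All non-responders will complete the second-stage randomization to either: 1) continue with assessments only; or 2) switch to the other intervention". Responders have assessments only from then on. The visit may be completed up to 30 days late.

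The SAP (PRISM primary and secondary outcomes) first tabulates baseline characteristics by first-stage arm. Step two collapses intervention assignment into "MI-only (arms D and E), CM-only (arms A and B), and MI+CM (arms C and F"). Step three gives descriptive six-month outcomes by those three groups; the SAP states "we did not conduct statistical tests or comment on the magnitude of CM, MI, or MI+CM effects". Step four looks at correlates of verified PrEP use without regard to either randomization.

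The arm letters refer to Figure 1, which is not shown. The text of neither document says how a man who misses month 3 or declines the second consent is grouped, what the denominators are, or how unobserved outcomes are treated.

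**The concern.** A percentage needs a defined denominator, and here the denominator seems to depend on an event three months after randomization. A man must attend month 3 within its window and also consent again before he can be classified. The protocol expects missed visits, since its Feasibility paragraph plans to count them.

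The protocol's Quantitative Analyses paragraph defines the primary outcome as PrEP medical evaluation over the six months from first-stage randomization. That period starts for every randomized man, classified or not. A man in the CM arm could even have a documented evaluation, through the incentive scheme, and then miss month 3.

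Two treatments of unclassified men are open, and the SAP does not choose between them. Leaving them out makes the results conditional on reaching month 3. Counting them by intervention received puts all of them into MI-only or CM-only, so the three groups carry loss differently by construction. Either way, the baseline table by first-stage arm and the outcome table may cover different men without the reader being able to tell. These are the SAP's only outcome results by intervention.

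**Working it through.** **Arm structure.** There are two first-stage arms and three month-3 paths (responder; non-responder on assessments only; non-responder who switches): 2 × 3 = 6 cells. The SAP uses six letters, with two arms in each single-intervention group and two in MI+CM. That fits responder plus stayer from each side, and one switch arm from each side. All six cells are then used, and none is for a man without month-3 status. The mapping is inferred from the group names.

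**Is there a figure to reproduce?** No. The protocol gives the size, "We will conduct a pilot SMART with 70 HIV-negative, stimulant-using MSM who meet CDC criteria for PrEP eligibility", but states "Because this is a pilot study, we have not conducted a formal power analysis". Neither document gives a dropout, response or uptake rate. What follows is illustrative.

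**Assumptions, none from the documents.** 1:1 allocation at both randomizations (35 per first-stage arm); 20% without month-3 status; 30% response among classified men; 20% later uptake among non-responders; the same rates in both arms; no further loss by month 6.

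**Pooled uptake.**
- Unclassified: 0.20 × 70 = 14. Classified: 56.
- Responders: 0.30 × 56 = 16.8. Non-responders: 39.2.
- Uptake: 16.8 + 0.20 × 39.2 = 24.64.
- Among classified men: 24.64/56 = 44%.
- Over all randomized, unobserved = no: 24.64/70 = 35%.
- Over all randomized, unobserved = yes: (24.64 + 14)/70 = 38.64/70 = 55%.

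Each first-stage arm gives the same bounds: 12.32/35 = 35% and 19.32/35 = 55%.

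**Range over month-3 loss m.** The lower bound is 0.44(1 − m); the upper bound is 0.44(1 − m) + m.

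| Loss m | Unclassified of 70 | Uptake, classified | Lower, all 70 | Upper, all 70 |
|---|---|---|---|---|
| 5% | 3.5 | 44% | 42% | 47% |
| 10% | 7 | 44% | 40% | 50% |
| 20% | 14 | 44% | 35% | 55% |
| 30% | 21 | 44% | 31% | 61% |

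**By SAP group, 20% loss.** Non-responders split into 19.6 stayers and 19.6 switchers.
- MI-only and CM-only together, unclassified men left out: 16.8 + 19.6 = 36.4 men; uptake (16.8 + 0.20 × 19.6)/36.4 = 20.72/36.4 = 57%.
- The same groups with the 14 counted in: 50.4 men, of whom 14/50.4 = 28% are unclassified; uptake 20.72/50.4 = 41% if none started and 34.72/50.4 = 69% if all did.
- MI+CM: 19.6 men, no unclassified men under either treatment; uptake 3.92/19.6 = 20%.

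**The case against.** A reader might infer that these men are excluded from the outcome results. The documents do not support that. The SAP excludes nobody and states no denominator. A man assigned only MI and never re-randomized could reasonably be called MI-only, and the SAP's Acceptability paragraph describes study arm simply as MI, CM or MI+CM. Step four is not tied to the letters, so he could appear there too. Figure 1 might also show where he goes.

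A reader might also infer that dropping these men overstates uptake, or that counting them in lowers the single-intervention groups. Both hold only if unclassified men started PrEP less often than the others. Nothing in the documents establishes that, and the bounds lie on both sides of the classified figure.

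Two further objections carry weight. Month-3 loss is not the main reason the three groups differ: every responder falls in a single-intervention group by construction, which alone gives 57% against 20% in the example. And the SAP plans no between-group tests, while its Feasibility paragraph promises randomization and follow-up rates, so overall loss will be visible.

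These objections limit the strength of the point but leave the gap. Follow-up rates do not say who is in each group's denominator, step four gives no result by intervention, and placement under the single intervention received is an unstated choice that affects two groups and never the third.

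**Conclusion.** The concern stands in limited form. The text gives randomized men without month-3 status no place in the three outcome groups, and no result by intervention is planned with all randomized men in the denominator. That the arms are completed only at month 3 is a sound inference, not a confirmed fact.

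The number of men affected and the direction of any bias are unknown. At an assumed 20% loss, the 44% seen in 56 classified men is compatible with anything from 35% to 55% over all 70. The width of that interval equals the loss rate, so if almost everyone was classified the effect is small.

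Severity is moderate: no test or effect estimate rests on these percentages.

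**What to change.** In SAP steps two and three:
- Report PrEP evaluation and PrEP uptake as n/N randomized by first-stage arm, with every first-stage randomized man in N. Give a lower bound (unobserved = no) and an upper bound (unobserved = yes). An outcome documented before a man was lost counts as observed.
- Show, per first-stage arm, the number not classified at month 3.
- State whether those men are included in MI-only or CM-only; if they are, identify them separately within those groups.

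The three-group table can stay as a secondary description. The cost is some SAP wording and one extra table, with no new data collection. The downside is wider and possibly less favourable percentages.
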